### 3.4.2. Exclusion Criteria

Patients meeting any of the following exclusion criteria at screening will not be enrolled in the study:

## Statistical Analysis Plan

- Patients who have dyskinesia of a severity that would significantly interfere with their ability to participate or perform study procedures.
- Pregnant or lactating females or females wishing to become pregnant.
- Patients who have any known contraindication to the use of LD, including a history of malignant melanoma or a history of narrow-angle glaucoma.
- Patients who have had previous surgery for PD (including but not limited to cell transplantation) or plan to have stereotactic surgery during the study period. Patients who have had deep brain stimulation [DBS] will also be excluded unless the procedure was performed more than 6 months prior to study enrollment.
- Patients with a history of psychotic symptoms requiring treatment, or suicidal ideation or attempt within the prior 12 months.
- Patients who have cancer with the exception of the following: basal cell carcinoma or successfully treated squamous cell carcinoma of the skin; cervical carcinoma in situ; prostatic carcinoma in situ; or other malignancies curatively treated and with no evidence of disease recurrence for at least 3 years.
- Patients taking certain prohibited medications (see [protocol Section 9.4.2](#)).
- Patients with a history of drug or alcohol abuse within the prior 12 months.
- Patients with chronic obstructive pulmonary disease (COPD), asthma, or other chronic respiratory disease within the last 5 years
- Patients with any contraindication to performing routine spirometry or who are unable to perform a spirometry maneuver (see [Appendix 15](#) for a list of contraindications).
- Patients with a current history of *symptomatic* orthostatic hypotension despite adequate treatment.
- Patients with any condition that in the investigator's opinion would make patients unable to comply with study procedures or make them unsuitable for their participation in the study.
- Patients who have any clinically significant abnormality or finding from examination, tests, or history that may compromise patient safety. Potential issues of concern should be raised to the medical monitor during eligibility review.
- For new CVT-301 naïve patients, patients who have been treated with an investigational drug within 4 weeks or 5 half-lives (whichever is longer) prior to the beginning of the screening period (this includes investigational formulations of marketed products).

### 3.5. DETERMINATION OF SAMPLE SIZE

The study is planned to enroll 390 patients to ensure that approximately 290 patients will complete the 12 month study. The sample size of this study is designed in order to

## Statistical Analysis Plan

capture sufficient amount of safety data required for regulatory submissions and is not based on formal statistical calculations.

### 3.6. TREATMENT ASSIGNMENT & BLINDING

This study is a randomized, dose-level blinded, multicenter study of inhaled CVT-301 for the treatment of up to 5 OFF episodes per day in PD patients experiencing motor fluctuations (OFF episodes). Following completion of SV2 and prior to randomization (for CVT-301-003, CVT-301-009, CVT-301-005 and other CVT-301-naïve patients), eligibility criteria will be reviewed by delegated staff. Sites must leave a minimum of 5 days between randomization and Treatment Visit 1.

Before TV1, patients will be assigned/randomized to treatment group [Dose Level (DL) 1, or 2]. Patients who received DL1 (target nominal dose of 35 mg LD FPD) in the CVT-301-004 study will receive DL1 (target nominal dose of 35 mg LD FPD) in this study, and patients who received DL2 (target nominal dose of 50 mg LD FPD) in the CVT-301-004 study will receive DL2 (target nominal dose of 50 mg LD FPD) in this study. Patients who received placebo in the CVT-301-004 study, CVT-301-003 patients, CVT-301-009 patients, and CVT-301-naïve patients (including CVT-301-005 observational arm patients) will be randomized in a 1:1 ratio to DL1 or DL2.

Upon confirmation of eligibility, the site will randomize an eligible patient using the Interactive Web Response System (IWRS). Randomization will be differentiated by the patient's Hoehn and Yahr PD disease severity scale rating (<2.5 versus ≥2.5) to balance for disease severity across each treatment group and by screening spirometry (FEV1 <60% of predicted or FEV1/FVC ratio <70% versus FEV1 ≥60% of predicted and FEV1/FVC ratio ≥70%). For the patients who received placebo in CVT 301 004, the differentiation of CVT 301 004 will be used. Patients and site staff will be blinded to treatment group.

### 3.7. ADMINISTRATION OF STUDY MEDICATION

Prior to the self-administration of inhaled study treatment, study staff will ensure that patients are adequately trained on the use of the inhaler according to the Instructions for Use (IFU). The IFU will be provided to each patient and will be part of the permanent study record.

In order to blind the treatment group, study kits with identical number and appearance of capsules will be distributed to patients in the CVT-301 groups.

The patient, investigator, and study site personnel, the Sponsor, representatives of the Contract Research Organization (CRO) involved in monitoring, data management, or other aspects of the study, and Core Laboratories will be blinded to the inhaled treatment group.

## Statistical Analysis Plan

Except in the case of an emergency, the treatment group codes will not be available to the investigator, the study site personnel, representatives of the CRO, or the Sponsor until after the completion of the study and final data review. All randomization data will be kept strictly confidential and accessible only to authorized persons until the time of unblinding after the end of the study; for emergency unblinding, the site will access the IWRS or call the IWRS helpdesk. When the data file has been verified and the protocol violations have been determined, the drug codes will be made available for data analysis.

During inhaler training, patients will be instructed to use the inhalation system in accordance with the IFU which includes a breath hold of 5 seconds following each capsule inhalation. For the purposes of timing study assessments in the clinic, "Time 0" (T0) is defined as the time of completion of inhalation of the last capsule of inhaled study treatment administered (i.e., beginning of the final breath hold). In the event that a capsule needs to be re-inhaled, T0 is at the end of the re-inhalation administration.

During the treatment period, patients will self-administer inhaled study treatment (CVT-301 DL1 or CVT-301 DL2) up to 5 times daily to treat OFF episodes during their waking day.

### 3.8. STUDY PROCEDURES AND FLOWCHART

This study has 3 periods: screening period, treatment period, and follow-up period; and a total of 9 planned visits: 2 screening visits, 6 treatment visits, and 1 follow-up visit. The maximum anticipated duration of this study for patients from the CVT-301-004 study will be approximately 59 weeks, including the final spirometry and DLCO assessment which takes place 4 to 5 weeks following the treatment period. The maximum anticipated duration of this study for CVT-301-naïve patients and CVT-301-009 patients, including the screening period and the final spirometry and DLCO assessments, will be approximately 64 weeks.

CVT-301-naïve patients (including CVT-301-005 observational arm patients) will undergo a screening period (of up to 35 days) prior to randomization. The screening period may be extended an additional 7 days if repeat screening assessments are required. The screening period will consist of 2 scheduled clinic visits: Screening Visit 1 (SV1) and Screening Visit 2 (SV2). CVT-301-004 patients will not be required to undergo the screening visits and will undergo TV1 after a 1- to 14-day period (or longer if approved by the Sponsor) following Treatment Visit 4 (TV4) of the CVT-301-004 study.

Before patients return to the clinic for TV1, they will be randomized to treatment group (see section 3.6 for details). The treatment period includes 6 separate in-clinic visits

1003804

Civitas Therapeutics, Inc.

CVT-301-004E

SAP Version 2.0

## Statistical Analysis Plan

over approximately 52 weeks. The first dose of study drug will be given in the clinic at TV1. The subsequent visits during the treatment period take place as follows:

- TV2: Week 4;  $28 \pm 5$  days after TV1.
- TV3: Week 12;  $84 \pm 14$  days after TV1.
- TV4: Week 24;  $168 \pm 14$  days after TV1.
- TV5: Week 36;  $252 \pm 14$  days after TV1.
- TV6: Week 52;  $364 \pm 14$  days after TV1.

Patients who terminate the study early will complete TV6 and return for the Follow-up DLCO visit 4-5 weeks after TV6.

Refer to Protocol [Appendices 2 to 10](#) for tables of study assessments at each visit.

## Statistical Analysis Plan

### 4. ENDPOINTS

#### 4.1. PRIMARY ENDPOINT

The primary endpoints related to the primary objective of the study are the pulmonary safety measures, FEV1, FVC and FEV1/ FVC ratio, assessed over a 12 month period. FEV1, FVC and FEV1/FVC ratio will be recorded from the single “best test” (based on effort with highest summed FEV1 and FVC). Variables will include the absolute FEV1, FVC, and FEV1/FVC ratio and FEV1 and FVC expressed as % of predicted value. Changes from baseline (TV1) for each variable will be calculated at each subsequent visit.

Percent Predicted =  $100 * (\text{Observed}) / \text{Predicted}$ , where predicted values are calculated using the formulae by [Hankinson et al \(Spirometric Reference Values from a Sample of the General U.S. Population, 1999\)](#):

Caucasian males  $\geq 20$  years of age:

- FVC predicted =  $-0.1933 + 0.00064 * \text{age} - 0.000269 * \text{age}^2 + 0.00018642 * \text{height}^2$
- FEV1 predicted =  $0.5536 - 0.01303 * \text{age} - 0.000172 * \text{age}^2 + 0.00014098 * \text{height}^2$

Caucasian females  $\geq 18$  years of age:

- FVC predicted =  $-0.3560 + 0.01870 * \text{age} - 0.000382 * \text{age}^2 + 0.014815 * \text{height}^2$
- FEV1 predicted =  $0.4333 - 0.00361 * \text{age} - 0.000194 * \text{age}^2 + 0.00011496 * \text{height}^2$

, Please see Hankinson et al (1999) for formulae for other races and age categories

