11.1.6. Spirometry

The following is a description of the pulmonary function testing at clinical sites and at dedicated pulmonary function facilities:

Pulmonary function will be measured by spirometry using the guideline specified by the Third National Health and Nutrition Examination Survey (NHANES III) ([Hankinson 1999](#)). Spirometry (with the exception of spirometry being performed in conjunction with DLco) will be performed by trained and qualified staff at each study site. Spirometry data collected by the study sites will be reviewed by a central spirometry laboratory [REDACTED] which will provide a quality over-read of all evaluations based on acceptability and repeatability metrics in accordance with ATS criteria ([Miller et al., 2005](#)). FEV₁, FVC and FEV₁/FVC ratio will be recorded from the single “best test” (based on effort with highest summed FEV₁ and FVC). Variables and comparisons will include the actual and expected forced FEV₁, FVC, and FEV₁/FVC ratio. Patients with FEV₁ <50% of predicted for race, age, sex, and height, or FEV₁/FVC ratio ≤60% in the ON state at screening will be excluded from the study. A pulmonologist will review the spirometry tracings/morphology of any patient with an FEV₁ that is ≥ 50% to <60% of predicted or an FEV₁/FVC ratio that is >60% to <70% at screening in order to determine eligibility. Patients with an FEV₁/FVC ratio that is >60% to <70% at screening will complete spirometry before and after the administration of a bronchodilator in a pulmonary function laboratory. Testing will be performed in accordance with the 2005 ATS/European Respiratory Society (ERS) criteria. The results of the bronchodilator challenge will be reviewed by a pulmonologist prior to potential randomization. Any CVT-301-naïve patients or [CVT-301-009](#) patients requiring pulmonary adjudication at screening will not be randomized until after full pulmonologist review.

Spirometry assessments will be done at the time points indicated in [Appendix 2](#) through [Appendix 10](#). The patient’s motor state at the time of each spirometry assessment will be recorded. At SV1, spirometry assessments should be done while the patient is in both the ON and OFF states. At SV2, spirometry assessments will be done only if a repeat measurement is needed for assessing eligibility.

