### Percent predicted of FEV1 and FVC

The percent predicted of FEV1 and FVC will be calculated using the following equation.

$$\text{Percent Predicted} = 100 * (\text{Observed}) / \text{Predicted}$$

where the predicted value is the value calculated based on formulae by [Hankinson et al \(1999\)](#). The details are listed in table below.

DLCO predicted , percent predicted of FEV1 and FVC	In case a variable used to calculate the predicted value (age, height, Hb) is missing, the following imputation rules will be used in order to calculate the predicted value:
Screening (prior to randomization)	Age, height or Hb from TV1 or the value closest to the date of DLCO/FEV1/FVC assessment if the value at TV1 is missing
TV3, within 2 weeks prior to 3	Age, height or Hb from TV3 or the value closest to the date of DLCO/FEV1/FVC assessment if the value at TV3 is missing
TV4, within 2 weeks prior to 6	Age, height or Hb from TV4 or the value closest to the date of DLCO/FEV1/FVC assessment if the value at TV4 is missing
TV5, within 2 weeks prior to 9	Age, height or Hb from TV5 or the value closest to the date of DLCO/FEV1/FVC assessment if the value at TV5 is missing
TV6, within 2 weeks prior to 12	Age, height or Hb from TV6 or the value closest to the date of DLCO/FEV1/FVC assessment if the value at TV6 is missing
4 to 5 weeks after TV6	The latest non-missing Hb closest to the date of DLCO/FEV1/FVC assessment taken.

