#### 9.1. SPIROMETRY

For CVT-301-naïve patients and [CVT-301-009](#) patients, spirometry will be assessed at the neurology sites for screening and TV1 and the pulmonary sites will be exclusively responsible for the conduct of spirometry after TV1 (within 2 weeks prior to the 3-, 6-, 9-, and 12-month visits, and 4 to 5 weeks following completion of Treatment Visit 6 [TV6]). For patients from [CVT-301-004](#), spirometry will be assessed at the neurology sites at TV1, and the pulmonary sites will be exclusively responsible for the conduct of spirometry after TV1 as described for the CVT-301-naïve patients. Spirometry data obtained in the study site will reviewed by a central spirometry laboratory (Biomedical Systems, Inc.) which will provide a quality over read of all evaluations based on acceptability and repeatability metrics in accordance with ATS criteria. FEV1, FVC and FEV1/FVC ratio will be recorded from the single “best test” (based on effort with highest summed FEV1 and FVC). Variables will include the absolute FEV1, FVC, and FEV1/FVC ratio and FEV1 and FVC expressed as % of predicted value.

The variables from pulmonary laboratory will include the FEV1, FVC, FEV1/FVC ratio, DLCO, IVC, SVC and VA. FEV1 and FVC expressed as % of predicted value, predicted DLCO, hemoglobin (Hb) adjusted predicted DLCO, and DLCO expressed as % of these predicted values will be calculated per the method in [section 6.2](#). The following analysis will be performed:

All the parameters collected at the pulmonary laboratory as well as the % of predicted DLCO and % of Hb adjusted predicted DLCO will be summarized descriptively by treatment group and overall. In addition, the data will be summarized by treatment/study group.

- Change from baseline to other visits for each parameter.
- Number and percentage of patients with FEV1/FVC < 60% and <70% by visit
- DLCO data will also be provided to indicate whether specific determinations met American Thoracic Society (ATS) quality criteria. The proportion of DLCO/spirometry data measurements meeting or not meeting ATS quality criteria will be summarized by treatment group and overall.

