### Sensitivity analyses of the spirometry data

The following sensitivity analysis will be performed for FEV1, FEV1/FVC and DLCO assessments.

- MI analysis: MI techniques based on Pattern Mixture Models (PMM) will be applied (Ratitch et al., 2011) as a further sensitivity analysis in the Safety population. This methodology will structure data based on missing data patterns. The method will be based on a missingness pattern having a monotone structure, i.e. if among the observations over time one data value is missing, all other values after this missing

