## Statistical Analysis Plan

### 10. INTERIM ANALYSES

Two interim analyses are planned. The first interim analyses were based on interim analysis SAP version 1.0 and data cut on Feb 10th, 2017. The second interim will be based on this SAP and planned data cut June 30, 2017.

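### The Caucasian female FVC equation in SAP 4.1 has a height-squared coefficient about 100 times too large, so FVC % predicted for these women would come out at about 1% or less if programmed as printed

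*SAP*

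**What the plan says.** Under the primary endpoint, SAP 4.1 states: "Variables will include the absolute FEV1, FVC, and FEV1/FVC ratio and FEV1 and FVC expressed as % of predicted value". Changes from baseline are to be calculated for each variable at each later visit. The section defines percent predicted as 100 × observed / predicted and prints four prediction equations, for FVC and FEV1 in Caucasian men and women. It refers to the cited reference-equation paper for other races and ages.

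The last term of the male FVC equation is "0.00018642 * \text{height}^2". The corresponding part of the female FVC equation is "0.000382 * \text{age}^2 + 0.014815 * \text{height}^2".

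SAP 6.2 returns to the derivation ("The percent predicted of FEV1 and FVC will be calculated using the following equation") and cites the same paper. It prints no coefficients; the table that follows deals only with missing age, height or hemoglobin. SAP 9.1 again requires "FEV1 and FVC expressed as % of predicted value, predicted DLCO, hemoglobin (Hb) adjusted predicted DLCO" to be calculated from the pulmonary laboratory data. So 4.1 is the only place in the SAP where this equation is written out.

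**The concern.** One of four parallel equations has a coefficient two orders of magnitude away from the rest. A predicted FVC of hundreds of litres is impossible, and it contradicts the female FEV1 equation on the next line.

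FVC is named in the primary objective, but the mixed model for the spirometry data and its multiple-imputation sensitivity analysis are specified for FEV1, FEV1/FVC and DLCO, not FVC. On the sensitivity analysis SAP 9.1 says: "The following sensitivity analysis will be performed for FEV1, FEV1/FVC and DLCO assessments". FVC is therefore assessed descriptively, in litres and as % predicted. If the printed line is what was programmed, the second form fails for every Caucasian woman. The level would look absurd. The change from baseline would look like almost no change, which is the unhelpful direction for a pulmonary safety study.

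**Working it through.** **Inputs.** The equations and the percent-predicted formula are from SAP 4.1. That section gives no height unit; protocol 11.1.1 records height in cm. The SAP gives no worked predicted value to reproduce, so the check is internal consistency.

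**Coefficients.** 0.014815 divided by each of the other three:
- male FVC: 0.014815 / 0.00018642 = 79.5
- male FEV1: 0.014815 / 0.00014098 = 105.1
- female FEV1: 0.014815 / 0.00011496 = 128.9

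**One woman, 65 years, 162 cm** (age² = 4225, height² = 26244):
- FVC as printed: −0.3560 + 0.01870×65 − 0.000382×4225 + 0.014815×26244 = −0.356 + 1.216 − 1.614 + 388.805 = 388.05 L
- FEV1 as printed: 0.4333 − 0.00361×65 − 0.000194×4225 + 0.00011496×26244 = 0.433 − 0.235 − 0.820 + 3.017 = 2.40 L
- Implied predicted FEV1/FVC: 2.40 / 388.05 = 0.6%

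A man of 65 years and 175 cm gets FVC 4.42 L and FEV1 3.30 L from the printed male pair, a ratio of 75%. For entry, protocol 11.1.6 says a patient with a "ratio ≤60% in the ON state at screening will be excluded from the study".

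**Units.** In inches the same woman gets FVC 59.5 L and FEV1 −0.15 L. In metres she gets −0.72 L and −0.62 L. Only centimetres make the other three equations work, and they do not rescue this one.

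**Coefficient divided by 100** (0.00014815, an assumption): 0.00014815×26244 = 3.888, so predicted FVC = 3.13 L and predicted FEV1/FVC = 2.40 / 3.13 = 76%.

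**Range over every integer age 45-75 and height 150-175 cm** (an assumed grid):

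| | As printed | With 0.00014815 |
|---|---|---|
| Predicted FVC | 332-453 L | 2.2-4.2 L |
| Predicted FEV1/FVC | 0.50-0.75% | 74-81% |
| Observed 3.0 L, % predicted | 0.66-0.90% | 71-134% |

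For comparison, the printed male pair gives a predicted ratio of 71-79% over ages 45-75 and heights 160-190 cm.

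**Change from baseline.** At 65 years and 162 cm, a fall of 0.30 L is 100 × 0.30 / 3.13 = 9.6 points with the rescaled coefficient and 100 × 0.30 / 388.05 = 0.08 points as printed, a factor of 124. Over the grid the factor runs from 107 to 149.

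**Pooled summaries, illustration only.** The documents give neither the share of Caucasian women nor the mean % predicted. Assume a share of 20-40%, a true mean of 95% and a factor of 124:
- 20% share: 0.80×95 + 0.20×95/124 = 76.2%
- 40% share: 0.60×95 + 0.40×95/124 = 57.3%

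A true 5-point fall in everyone would print as about 4.0 and 3.0 points respectively.

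**The case against.** Four arguments deserve weight.

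*It may be a PDF-reading fault.* The text was extracted by a program, and the anomaly amounts to two missing zeros. The other three coefficients came through with all their zeros, which makes this less likely, but only the original page can settle it.

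*The cited paper is the specification.* The SAP says predicted values come from that paper, and a programmer must open it for other races. Someone coding from it would avoid the error. The documents do not show which source was used, and the printed line is still wrong as an instruction.

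*It would be noticed.* Values near 1% of predicted beside plausible FEV1 percentages should be caught when outputs are reviewed under SAP 13. That is probably true of the levels, and so the pooled means above are unlikely to survive to a report. It does not make the formula right.

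*The reach into tables is uncertain.* The sentence in SAP 9.1 on what will be summarized names % predicted only for DLCO, and no spirometry table title names FVC % predicted. This stands. The variable is required and its change must be calculated, but whether it appears inside the tables titled for FEV1 and FVC cannot be seen from the index.

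A smaller point also stands: 1% is not a strict ceiling. At 65 years and 162 cm, 1% is reached at an observed FVC of about 3.9 L, or 124% of the rescaled prediction. A few women with large lungs would print slightly above 1%.

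**Conclusion.** The concern holds. As printed, the equation is wrong, and this follows from the SAP's own neighbouring equations and the recorded height unit. The effect is confined to FVC % predicted in Caucasian women, and to any pooled summary of that variable: levels of about 1% or less, and changes reduced by a factor of 107 to 149 over ages 45-75 and heights 150-175 cm.

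Absolute FEV1 and FVC, FEV1/FVC, FEV1 % predicted, eligibility, the randomization strata, and the mixed-model and imputation analyses are unaffected.

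That the coefficient is wrong is certain if the extracted text matches the page. That the right value is 0.00014815 is an inference from digits and scale. Whether any output was affected depends on what was programmed, which the documents do not show. It should be fixed, but it does not threaten the study's main conclusions.

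**What to change.** 1. Check the coefficient on the original SAP page, then against the cited reference-equation paper, and correct SAP 4.1. Do not adopt 0.00014815 without that check.
2. Confirm which coefficient is in the derivation program and was used for the interim outputs (data cuts of 10 February and 30 June 2017). The second is tied to this document: "The second interim will be based on this SAP and planned data cut June 30, 2017".
3. If the printed value was used, rerun FVC % predicted and its change from baseline for Caucasian women, and any pooled summary containing them.
4. While editing, state the height unit in 4.1. It gives none, and the DLCO equations in 6.2 use inches. A range check on predicted volumes is optional.

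The cost is one number in the SAP and one line of code to check, with a rerun of descriptive summaries only if step 2 shows that the printed value was used.
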